7.6.2 Procedures and Follow-up after Treatment Discontinuation

The evaluation during which the Investigator determines that SL-401 will be discontinued should be considered the End of Treatment Evaluation; all tests and procedures for the End of Treatment Evaluation are listed in [Table 6](#) and [Table 8](#) (in [Section 9.8](#)). In addition, patients should be followed for a minimum of 30 days after the last infusion of SL-401 for assessment of AEs (including potential new AEs and potential change/resolution of existing AEs).

If the patient is in CR/PR at the time of discontinuation, disease assessments should continue to be performed as described in [Section 8.12](#) on an every 6-week basis (± 1 week) through 6 months post-C1D1 and then on an every 90-day basis or until, in the judgment of the Investigator, there is evidence of relapsed or progressive disease. Beyond the End of Treatment Evaluation and 30-day follow up (safety/AE assessment), it is requested that subsequent follow-up occur approximately every 90 days for survival status. (If the patient is in CR/PR at the time of discontinuation, disease assessments should continue to be performed as described in [Section 8.12](#) on an every 6-week basis (± 1 week) through 6 months post-C1D1 and then on an every 90-day basis or until, in the judgment of the Investigator, there is evidence of relapsed or

progressive disease. Patients who undergo SCT will be followed for the occurrence of VOD and engraftment delay or failure as part of survival monitoring.

If the patient discontinues SL-401 treatment and also withdraws consent for collection of future information, no further evaluations should be performed and no additional data should be collected as part of the study. The Sponsor will only retain and use any data collected before withdrawal of consent.

Please consult [Section 6.4](#) for recommendations concerning ongoing follow-up of patients alive with or without evidence of disease progression at the time of Study Completion/assessment of primary and critical secondary endpoints.

8 Study Procedures

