9.6 Safety Monitoring: Through 30 Days after Last Infusion

All Patients, All Study Stages:

- AE and SAE monitoring
- Survival status

9.7 Survival Monitoring: Approximately Every 90 Days after End of Treatment until Study Completion

Patients in PR/CR at End of Treatment:

- Survival status and response/disease progression status, continuing until assessments of the primary and secondary objectives are completed for all patients; survival status may be performed by telephone contact.
- Patients who undergo SCT will be followed for the occurrence of VOD and delayed or failed engraftment as part of survival monitoring.

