10.1.1 Adverse Event (AE)

An AE is any untoward medical occurrence in a study patient who is administered a medicinal product (drug or biologic); the event may or may not have a causal relationship with the medicinal product. Examples of AEs include, but are not limited to the following:

- Clinically significant symptoms and signs including:
 - Worsening of signs and symptoms of the disease under study; disease progression without worsening of signs and symptoms as assessed by bone marrow aspiration or other methods should not be reported as AEs.
 - Signs and symptoms resulting from drug overdose, abuse, misuse, withdrawal, sensitivity, dependency, interaction, or toxicity.
 - All possibly related and unrelated illnesses, including the worsening of a preexisting illness.
 - Injury or accidents. Note that if a medical condition is known to have caused the injury or accident (hip fracture from a fall secondary to dizziness), the medical condition (dizziness) and the outcome of the accident (hip fracture from a fall) should be reported as 2 separate AEs.
- Abnormalities in physiological testing or physical examination findings that require clinical intervention or further investigation (beyond ordering a repeat confirmatory test).
- Laboratory abnormalities that meet any of the following (Note: merely repeating an abnormal test, in the absence of any of the below conditions, does not constitute an AE. Any abnormal test result that is determined to be an error does not require reporting as an AE):
 - Test result that is associated with accompanying symptoms
 - Test result that requires additional diagnostic testing or medical/surgical intervention
 - Test result that leads to significant additional concomitant drug treatment or other therapy
 - Test result that is considered to be an AE by the Investigator or Sponsor

Note that VOD, engraftment delay or failure occurring post-SCT and any changes in visual acuity and/or color vision will be followed as adverse events of special interest.

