4.4.2. Adverse Events

All AEs will be coded using the MedDRA coding system and displayed in tables and data listings using system organ class (SOC) and preferred term.

Analyses of AEs will be performed for those events that are considered treatment-emergent, where treatment-emergent is defined per protocol as any AE with onset after the first administration of tagraxofusp through 30 days after the last dose of tagraxofusp, or any event that was present at baseline but worsened in intensity or was subsequently considered drugrelated by the Investigator through 30 days after the last dose of tagraxofusp.

The number and percentage of patients with any treatment-emergent AE (TEAE), common AEs (defined as occurring in $\geq 10\%$ of the study sample), with any TEAE assessed by the Investigator as related to treatment, with TEAE occurring within 24 hours of infusion, with any TEAE with severity \geq Common Terminology Criteria for Adverse Events (CTCAE) Grade 3, with any serious adverse event (SAE), with any AE leading to discontinuation of study treatment, with any AE to dose reduction, and with any AE leading to dose interruption will be summarized by disease, line of therapy, dose and overall. In these tabulations, each patient will contribute only once (ie, the most related occurrence or the most intense occurrence) to each of the incidence rates in the descriptive analysis, regardless of the number of episodes.

Treatment-emergent AEs summarized by patient incidence rates are not tabulated by severity or relationship to study treatment; therefore, in such tabulations, a patient contributes only once to the count for a given AE SOC or preferred term. For tabulations that include classification by relationship to study treatment, AEs with missing relationship will be considered related to study drug. For tabulations that include classification by maximum severity grade, AEs with missing CTCAE severity will be included in a category for missing severity.

Incidence of TEAEs occurring within 24 hours of infusion will be summarized by SOC and preferred term.

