Analysis of AEs over time will be conducted by presentation of AE incidence by cycle. For this analysis, incidence per cycle will be based on the onset of a particular preferred term event within the cycle, where onset is indicated by first or repeat occurrence or increase in severity of the event within that cycle. This analysis will be conducted for all AEs and for AEs of Grade ≥ 3 severity. For AEs of special interest, Kaplan-Meier analyses of time to first occurrence of Grade ≥ 2 severity will be conducted for FL BPDCN, R/R BPDCN, and AML patients.

AESI's will be determined using MedDRA version 19.0 standardized medical queries (SMQs), high-level terms, or preferred terms, as follows:

- Possible hypersensitivity events, based on the SMQ Hypersensitivity (broad search).

- Vascular capillary leak syndrome (CLS), based on the MedDRA SMQ [to be provided] in addition to preferred terms of hypoalbuminaemia, blood albumin decreased, and proteinuria.
- Visual acuity, based on the MedDRA preferred terms of visual acuity reduced, visual acuity reduced transiently, visual acuity tests abnormal.
- Post-transplantation veno-occlusive disease, based on the MedDRA preferred terms pulmonary veno-occlusive disease and veno-occlusive liver disease.
- Possible drug-induced liver injury events, based on the SMQ drug-related hepatic disorders (broad search).

Summary tables of AESIs produced will report AESI by preferred term, causality, severity grade, seriousness, and whether AESI led to discontinuation. These tabulations will be completed for all patients, by line of therapy for BPDCN patients, AML patients, and indication. AESIs will also be included in data listings.

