8.3. Capillary Leak Syndrome FDA Algorithm

Screen-positive subjects include those

- a. With Preferred Term “Capillary leak syndrome” as an adverse event, OR
- b. Those meeting 2 or more of the criteria in the table below with at least 2 criteria having a start date within 7 days of each other.

Criteria	Variable	Value
		Hypoalbuminaemia
≥ 1 of these (Hypoalbuminemia)	PT	
	Lab result	Albumin (any value ≤ 3 g/dL)
	HLT	Oedema
	PT	Ascites
	PT	Eyelid oedema
	PT	Face oedema
	PT	Fluid overload
	PT	Fluid retention
	PT	Generalized oedema
	PT	Hypervolaemia
	PT	Laryngeal oedema
	PT	Oedema
	PT	Oedema peripheral
	PT	Periorbital oedema
	PT	Peripheral swelling
	PT	Swelling
	PT	Swelling face
	PT	Weight increased
	VS result	Weight (any value > 5 kg from baseline)
≥ 1 of these (Hypotension)	PT	Hypotension
	PT	Hypovolemia
	VS result	Systolic Blood Pressure (any value < 90 mmHg)
	Concomitant medication	Dopamine
	Concomitant medication	Ephedrine
	Concomitant medication	Epinephrine
	Concomitant medication	Norepinephrine
	Concomitant medication	Norepinephrine bitartrate
	Concomitant medication	Phenylephrine

	Concomitant medication	Vasopressin
≥ 1 of these (CRS/IRR)	PT	Cytokine release syndrome
	PT	Infusion related reaction
("Catch-all")	PT	Cardiac arrest
	PT	Cardiopulmonary failure
	PT	Multi-organ failure
	PT	Multiple organ dysfunction syndrome

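### The SAP tables stop counting post-transplant VOD 30 days after the last dose and omit engraftment failure, and the capillary leak AESI counts isolated low albumin

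*SAP*

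**What the plan says.** **Window.** SAP 4.4.2 states: "Analyses of AEs will be performed for those events that are considered treatment-emergent". That status covers "any AE with onset after the first administration of tagraxofusp through 30 days after the last dose of tagraxofusp", plus baseline events that worsen or are later judged drug-related within the same limit.

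**VOD.** The AESI list in the same section has the entry "Post-transplantation veno-occlusive disease, based on the MedDRA preferred terms pulmonary veno-occlusive disease and veno-occlusive liver disease". It gives no separate window, time origin or denominator. SAP 4.4 runs safety tables on the Safety Population, and 4.4.2 asks for AESI tables for all patients, by line of therapy and for AML.

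**Protocol on the same events.** Section 10.1.1 puts these events in its special-interest class: "VOD, engraftment delay or failure occurring post-SCT and any changes in visual acuity and/or color vision will be followed as adverse events". Section 7.6.2 says: "Patients who undergo SCT will be followed for the occurrence of VOD and engraftment delay or failure as part of survival monitoring". Section 9.7 repeats this, with contacts about every 90 days until study completion. Section 3.8 gives the purpose of the VOD follow-up, added by Amendment 9: to find out whether SL-401 changes VOD risk after a later SCT. Engraftment follow-up came with Amendment 12.

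**CLS.** The SAP AESI is a MedDRA query whose name is still a placeholder, "in addition to preferred terms of hypoalbuminaemia, blood albumin decreased, and proteinuria". SAP 4.4.2.1 compares the demographics of patients with and without this AESI, and adds analyses on an FDA algorithm. Under that algorithm (Section 8.3) a patient screens positive with the CLS preferred term, or by meeting several criteria that start close together: "Those meeting 2 or more of the criteria in the table below with at least 2 criteria having a start date within 7 days".

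**The concern.** Post-transplant events happen after an SCT that itself follows the last infusion. A window anchored on the last infusion therefore cuts off post-transplant time, by an amount that depends on how soon the SCT took place. A denominator of all treated patients adds people who were never at risk. The protocol poses a specific safety question about transplanted patients, and no planned table answers it. For engraftment delay or failure there is no planned analysis at all, although Protocol 10.5 treats these reports as 15-day safety reports.

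CLS was the principal dose-limiting toxicity (Protocol 3.8). If one low-albumin term places a patient in the CLS group, a comparison of patients with and without CLS partly compares patients with and without low albumin. With the query left blank, the definition is also unfinished in an open-label study.

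**Working it through.** **1. Post-transplant time that the tables cover.** The window closes 30 days after the last infusion. For an SCT g days after that infusion, the covered post-transplant time is max(0, 30 − g). The documents do not give g, so these values are assumptions that show the range:

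- g = 7: 30 − 7 = 23 days
- g = 14: 16 days
- g = 21: 9 days
- g = 28: 2 days
- g = 30 or more: 0 days

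**2. Against the protocol's visit schedule.** With the last infusion on Day 5, the window closes on cycle Day 5 + 30 = 35. The end-of-cycle assessment is on Day 21 ± 7, that is Day 14 to 28, which leaves 35 − 28 = 7 to 35 − 14 = 21 days in the window. If held infusions push the last dose to Day 10, the window closes on Day 40 and 12 to 26 days remain. Survival contacts come about every 90 days, so the follow-up in which the protocol looks for these events runs far beyond the window.

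**3. AESI lists side by side.**

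- VOD: in the protocol and in the SAP (two preferred terms).
- Engraftment delay or failure: in the protocol; no SAP term.
- Visual acuity: in both.
- Color vision: in the protocol; no SAP term.

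The SAP takes its objectives from Amendment 9 (SAP 1.1.2). That would explain the missing engraftment item, but it does not supply one.

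**4. Reach of the CLS AESI.** Protocol 3.7.2 reports hypoalbuminemia as a treatment-emergent event in 42% of 26 BPDCN patients. Only 11/26 = 42.3% rounds to 42% (10/26 = 38.5%, 12/26 = 46.2%). The exact 95% interval is 23.4% to 63.1%. If those events carry the hypoalbuminaemia preferred term, all 11 patients meet the AESI definition on that term alone, so the AESI rate is at least 42.3%. Study 50047 points the same way: 58.7% of 92 is 54 patients with hypoalbuminemia attributed to SL-401.

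**5. What cannot be computed.** The documents do not say how many of the 11 had hypoalbuminaemia alone. They also do not give non-serious CLS counts or co-occurring criteria, so no rate under the Section 8.3 algorithm can be derived.

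**The case against.** **On VOD.** The 30-day limit is also the protocol's own rule for summarising adverse events (Section 12.5). Serious and related events are collected after day 30 (Section 10.2), and SAP 3.11 lists everything on the eCRF. Late VOD is therefore untabulated, not lost. That is correct, and the defect lies in the tables, not in data collection. But listings give no rate, no denominator and no time from SCT, so the protocol's question stays unanswered.

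A reader might infer that the VOD table must come out close to zero. The documents do not support this: neither the lag to SCT nor the timing of VOD is given, and an early SCT leaves up to about three weeks inside the window. A reader might also gauge the dilution from the 6 of 16 bridged patients in Protocol 3.7.2. Those 6 are only the progression-free bridged patients in one first-line, one-dose subgroup, so they do not give a transplant rate for the safety tables.

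**On CLS.** The SAP already plans analyses on the Section 8.3 algorithm. It tabulates AESIs by preferred term, so hypoalbuminaemia can be separated, and it limits the AESI Kaplan-Meier analysis to Grade 2 or higher. Only the demographic comparison names the AESI definition; the count, onset and resolution summaries say CLS without naming a definition. A broad search is also in keeping with the protocol, which describes hypoalbuminemia and edema as manifestations of CLS. All of this stands, and it rules out saying that the SAP as a whole measures CLS wrongly.

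It is tempting to set 11/26 against the 2/26 with serious CLS and call the AESI inflated. That compares any-grade events with serious events only. Nor is the algorithm certain to give a low rate: it accepts any albumin value of 3 g/dL or less and any of several edema terms, and peripheral edema alone was reported in 46% of the same 26 patients.

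**Conclusion.** The point holds in two limited parts.

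First, as written, SAP 4.4.2 tabulates post-transplant VOD only to day 30 after the last dose, over all treated patients, and leaves engraftment delay or failure and color vision off the AESI list. This rests on the plain text: a general rule with no stated exception. The loss of post-transplant time is complete when the SCT comes 30 or more days after the last infusion and partial before that; its actual size depends on a lag that the documents do not give.

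Second, the CLS AESI admits a patient on one albumin or proteinuria term, its query is blank, and the SAP does not say which CLS definition is the main one. The demographic comparison therefore includes any patient whose only qualifying event is hypoalbuminaemia. The 11/26 shows how common the term is, not how far CLS is overstated.

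This should be fixed, but it is not critical. These are descriptive safety tables in an updated report, and no hypothesis test or primary endpoint depends on them.

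**What to change.** - Exempt post-SCT VOD and engraftment delay or failure from the 30-day rule. Summarise them among transplanted patients, from the SCT date to last follow-up. The SAP already separates bridged from non-bridged patients for efficacy (Section 3.9).
- State which patients were enrolled before systematic follow-up began. Amendment 9 is dated 09 February 2017, inside the Stage 3 enrollment period of 26 October 2016 to 17 March 2017. Amendment 12 refers to the approved package insert, so it is no earlier than 21 December 2018, while Stage 4 enrollment ended on 7 January 2019. At most the last 17 days of enrollment (10 in December, 7 in January) could fall under it. Earlier VOD and engraftment data may be incomplete, and the table should say so.
- Add engraftment delay or failure and color vision to the AESI list, with their preferred terms.
- Fill in the CLS query. For the main CLS summaries and the demographic comparison, classify patients by the CLS preferred term or the Section 8.3 algorithm. The algorithm screens patients and does not date events, so add a rule for onset and resolution dates.
- Report isolated hypoalbuminaemia and proteinuria separately.

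The cost is SAP wording and a few extra tables. Reported VOD rates may rise.

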3.7.2 Current Study (STML-401-0114)

Stage 1 of STML-401-0114 employed a traditional 3+3 design and has been completed. A total of 23 patients were enrolled in Stage 1, of whom 9 had BPDCN and 14 had R/R AML. SL-401 was investigated at doses of 7, 9, 12, and 16 µg/kg/day IV for up to 5 consecutive days every 21 days (i.e., a multi-cycle regimen). (Only patients with AML received SL-401 at doses of 9 and 16 µg/kg/day.) The maximum tested dose of SL-401 in patients with BPDCN was 12 µg/kg/day; an MTD was not identified in BPDCN.

A complete summary of all AEs attributed to SL-401, including DLTs seen in Stage 1 of the study, is available in the most recent version of the SL-401 Investigator Brochure.

An analysis of safety data available through 28 July, 2016, for 26 patients with BPDCN showed that, overall, 24 (92%) patients have experienced at least 1 treatment-emergent adverse event (TEAE), with 22 (85%) patients experiencing at least 1 ≥Grade 3 TEAE. The most common TEAE was transaminase elevation (either ALT increased [62%] or AST increased [58%]). Overall, 17 (65%) patients have experienced ALT increased and/or AST increased, with these events also being the most common ≥Grade 3 TEAE (each 54%), treatment-related TEAE (54%), and treatment-related ≥Grade 3 TEAE (50%). Transaminase elevations were largely transient and not dose-limiting.

Other most commonly reported TEAEs, regardless of relationship to study drug, were nausea and peripheral edema (each 46%); fatigue, hypoalbuminemia, and pyrexia (each 42%); chills (35%); and anemia and hyperglycemia (each 31%).

The frequency and type of TEAEs were similar between the 12 µg/kg/day and 7 µg/kg/day dose groups, with no indication of dose-relationship.

Twelve (46%) of 26 patients experienced at least 1 serious adverse event (SAE). The only SAEs reported for >1 patient were CLS, pyrexia, and respiratory failure (each 2 patients).

Please consult the most recent SL-401 Investigator Brochure for comprehensive and up-to-date information concerning the safety profile associated with SL-401.

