Denileukin diftitox also is associated with loss of visual acuity, usually with loss of color vision, with or without retinal pigment mottling. Recovery was reported in some of the affected patients; however, most patients reported persistent visual impairment. This finding is considered related to the IL-2 component of denileukin diftitox. Although SL-401 targets IL-3R rather than IL-2R, patients will be monitored for potential vision loss in this study.

SL-401 was granted Breakthrough Therapy Designation (BTD) by the US FDA for the treatment of BPDCN in August 2016. In October 2016, the Sponsor conducted an interim analysis of efficacy data from 32 patients with BPDCN enrolled in this study between 06 October, 2014, and 29 August, 2016. A meeting was held with FDA on 20 December, 2016, to review the results of this interim analysis and discuss the continued development of SL-401 for treatment of BPDCN. As an outcome of that meeting, the following changes were made by Amendment 9:

- Enrollment of patients with AML is closed.
- Enrollment of patients with BPDCN is ongoing.
 - Any patient with first-line BPDCN enrolled in this study on or after 26 October, 2016, is included in Stage 3; a sufficient number of patients will be enrolled to ensure 10 evaluable patients are included, with evaluable patients being those with a diagnosis of BPDCN, as confirmed via central pathology review who received at least 1 dose of SL-401. These patients will constitute a standalone pivotal cohort for confirmation of efficacy of SL-401 in first-line BPDCN; for reference in this

protocol, this cohort will be designated Stage 3. The primary endpoint for this pivotal cohort is the CR rate.

- Any patients with R/R BPDCN enrolled in this study on or after 26 October, 2016, are allocated to Stage 4. After the maximum number of planned first-line BPDCN patients are enrolled in Stage 3, any additional first-line BPDCN patients are to be enrolled in Stage 4. BPDCN patients enrolled in Stage 4 subsequent to completion of enrollment in Stage 3 will receive the lyophilized formulation of SL-401 for Injection.
 - Enrollment will continue in Stage 4 until the study enrollment cap is reached.
- The total study sample size is increased to up to 120 patients (including ~70 patients with BPDCN) in order to adequately assess efficacy and safety of SL-401 in patients with BPDCN in a clinical study setting.

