- The inclusion/exclusion criteria for patients with BPDCN and SL-401 dose and treatment schedule are the same across Stages 2-4, with the exception that only first-line BPDCN patients are eligible for Stage 3.
- Safety monitoring to assess visual acuity and color vision, which are potential class toxicities of immunotoxins, and follow-up to determine whether treatment with SL-401 alters the risk of veno-occlusive disease (VOD) after subsequent SCT have been added. Other study procedures and evaluations are the same across Stages 2-4.

Key elements included in Protocol Amendment 10 are as follows:

- The total study sample size is increased to up to 130 patients (including ~80 patients with BPDCN) in order to ensure continued access to SL-401 for BPDCN patients in a clinical study setting.
- Updated enrollment status.
- Updated guidance for toxicity management, including CLS management, to continue reducing the risk of severe CLS and other SL-401-associated toxicities.
- Updates to reflect agreements and requests made by the FDA, including agreements on the primary efficacy endpoint for Stage 3.

Protocol Amendment 11 provides for additional BPDCN patients to be enrolled in Stage 4.

Protocol Amendment 12 provides details on the timing of analyses of duration of response and overall survival for all cohorts, as well as modifications to certain procedures based on the approved package insert and follow up requirement for patients who received stem cell

transplant following treatment with SL-401, to identify engraftment delays or failures. SL-401 Injection frozen solution (1mg/mL) was approved by the Food and Drug Administration (FDA) on 21 December 2018 for the treatment of BPDCN in adults and in pediatric patients 2 years and older under the name ELZONRIS (tagraxofusp-erzs).

4 Study Objectives

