8.11 Vision Assessment

All patients will be questioned regarding any changes in visual acuity and/or color vision. Patients who have experienced any \geq Grade 2 study drug-related changes in vision (NCI CTCAE v4.03 Grade) will have an ophthalmologic consultation and/or examination performed. In the event any abnormalities are detected, the patient will be followed up as per the recommendations of the consulting ophthalmologist. Management of treatment-related ocular disorders with inflammatory characteristics should include corticosteroid eye drops and/or other measures, as indicated by an ophthalmologist. In the setting of persistent study drug-related ocular disorders \geq Grade 2, consultation with the study's Medical Monitor is required.

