1.1.2. Study Objectives

The following objectives are defined in the Study Protocol (Amendment 9, 09 February 2017). The response criteria referenced throughout the Study Objectives are provided in [Section 8](#).

Primary objectives for Stages 1, 2, 3, and 4 are as follows:

Stage 1: The objectives of Stage 1 are to:

- Determine the maximum tolerated dose (MTD), or the maximum tested dose where multiple dose limiting toxicities (DLTs) are not observed, of tagraxofusp.

Stage 2: The objectives of Stage 2 are to:

- Determine the efficacy of tagraxofusp in patients with BPDCN, as assessed by objective response rate (ORR).
- Characterize the safety profile of tagraxofusp at the MTD or maximum tested dose in both patients with AML and BPDCN.

Stage 3: The objectives of Stage 3 are:

- Determine the complete response (CR) rate (ie, CR + CR with incomplete blood count recovery [CRI] + CR [clinical] with minimal residual skin abnormality [CRC]) in patients with first-line BPDCN. Note that these objectives are supported by prespecified statistical hypotheses and were evaluated using appropriate statistical inference during the initial reporting of this study.
- Characterize the safety profile of tagraxofusp in patients with first-line BPDCN.

Stage 4: The objectives of Stage 4 are to:

- Further characterize the efficacy of tagraxofusp in first-line and R/R patients with BPDCN following the completion of Stage 2 and Stage 3 as assessed by the rate of CR (CR + CRI + CRC).
- Further characterize the safety profile of tagraxofusp among first-line and R/R patients with BPDCN.
- Characterize the efficacy and safety of a lyophilized formulation of tagraxofusp among first-line and R/R patients with BPDCN.

Secondary objectives include:

- Determine the CR rate (CR + CRI + CRC) for Stage 1 and 2 patients, and ORR for Stage 3 patients.

- Estimate duration of response (DOR), progression-free survival (PFS) and overall survival (OS) in patients with BPDCN. Note that for patients that received a stem cell transplant (SCT), duration of response includes time pre- and post-SCT.
- Enable preliminary characterization of the estimated ORR in patients with R/R AML, including subsets of patients with R/R AML categorized by pre-treatment blast counts, cytogenetics, or CD123 measurement.
- Estimate DOR, PFS, and OS in patients with AML.
- Characterize the pharmacokinetics (PK) and immunogenicity of tagraxofusp.

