4.4. Safety Analyses

With the exception of Subgroup Analyses ([Section 3.9](#)), all safety tabulations will be presented by disease (first-line BPDCN, R/R BPDCN, AML) for all patients in the Safety Population by stage of enrollment (all doses included). All safety tabulations will be presented for first-line BPDCN patients in the Safety Population who were treated at 12 µg/kg/day by stage of enrollment and for those treated with lyophilized formulation of tagraxofusp.

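### Directed vision questioning began only with Amendment 9, but the SAP's visual-acuity AESI tables pool and compare patients from before and after it without allowing for the change

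*SAP*

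**What the plan says.** **When vision monitoring started.** Protocol 3.8 introduces a list with "As an outcome of that meeting, the following changes were made by Amendment 9". One item on that list is "Safety monitoring to assess visual acuity and color vision, which are potential class toxicities of immunotoxins", described as having been added. SAP 1.1.2 dates Amendment 9 to 09 February 2017. Another item is "Enrollment of patients with AML is closed".

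**What was added.** Protocol 8.11: "All patients will be questioned regarding any changes in visual acuity and/or color vision". An ophthalmology consultation or examination follows for drug-related changes of Grade 2 or higher. A vision row appears in Protocol Tables 7 and 8 (BPDCN, Stages 2-4) but not in Tables 5 and 6 (Stage 1 and Stage 2 AML). The visit text in Protocol 9.3.5, 9.4.5 and 9.5, by contrast, places vision monitoring under all patients and all stages.

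**How the SAP tabulates it.** SAP 4.4.2 defines the visual AESI by three visual-acuity preferred terms. Of the AESI tables it says: "These tabulations will be completed for all patients, by line of therapy for BPDCN patients, AML patients, and indication". It also plans Kaplan-Meier curves of time to first Grade 2 or higher AESI, separately for first-line BPDCN, R/R BPDCN and AML. The split by stage and formulation is not in that section. It comes from SAP 4.4, which requires every safety table for first-line BPDCN at 12 µg/kg/day to be shown "by stage of enrollment and for those treated with lyophilized formulation of tagraxofusp". Neither section mentions the change in how visual events were sought.

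**The concern.** A directed question about eyesight, backed by referral for Grade 2 or higher related changes, will usually bring out more visual events than an open question about health. The switch between the two is tied to calendar time, and so are stage and formulation. First-line Stages 1/2 received the frozen product and enrolled before the amendment. First-line Stage 4 received the lyophilized product and enrolled after it. In that contrast, formulation and ascertainment cannot be separated.

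Two readings are at risk. The all-patient rate of a toxicity that the protocol treats as a possible class effect may be understated. The lyophilized product may also appear to carry more visual toxicity than the frozen one when only the questioning changed. Characterizing the safety of the lyophilized formulation is a primary Stage 4 objective (Protocol 4.1), so the second reading matters.

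**Working it through.** The plan states no figure for this point, so there is nothing to reproduce. The check sets enrollment dates against the amendment and then sizes the possible effect.

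**Step 1: who enrolled when.**
- Stages 1/2 BPDCN: 32 patients, enrolled by 29 August 2016 (SAP 3.13.1; Protocol 12.10). All before the amendment.
- AML: enrollment closed by Amendment 9, so all before it. The final number is not given. Protocol 3.7.2 supplies a floor: "A total of 23 patients were enrolled in Stage 1, of whom 9 had BPDCN and 14 had R/R AML". The enrollment cap of about 145, including about 95 BPDCN, implies about 145 − 95 = 50. I use 50 as an assumption and 14 as the low end.
- Stage 3: 13 patients, 26 October 2016 to 17 March 2017 (SAP 3.1). Straddles 09 February 2017.
- Stage 4: 37 first-line patients treated, enrolled after 17 March 2017 (SAP 1.1, 3.1), all after the amendment. A further 5 R/R patients enrolled after 29 August 2016, some possibly before it.

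**Step 2: shares of the denominator.** Treated BPDCN = 32 + 13 + 37 + 5 = 87, counting all 32 and all 13 as treated. Enrolled before directed questioning: 32/87 = 37%. Adding all of Stage 3: 45/87 = 52%. Adding the 5 R/R Stage 4 patients as well: 50/87 = 57%.

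**Step 3: effect on the pooled rate.** Let p be the true incidence, N the number treated, m the number under directed questioning, and s the fraction of events captured by the general question relative to directed questioning. The observed rate is p × [m + s(N − m)] / N. Both p = 10% and s are assumptions, not document figures. Take m = 55 if Stages 3 and 4 all count as monitored (13 + 42), and m = 37 if only first-line Stage 4 does.

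| Denominator | m | s = 1 | s = 0.5 | s = 0 |
|---|---|---|---|---|
| All patients, 50 AML (N = 137) | 55 | 10.0% | 7.0% | 4.0% |
| | 37 | 10.0% | 6.4% | 2.7% |
| All patients, 14 AML (N = 101) | 55 | 10.0% | 7.7% | 5.4% |
| | 37 | 10.0% | 6.8% | 3.7% |
| BPDCN only (N = 87) | 55 | 10.0% | 8.2% | 6.3% |
| | 37 | 10.0% | 7.1% | 4.3% |

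Example: 0.10 × (55 + 0.5 × 82)/137 = 9.6/137 = 7.0%.

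**Step 4: effect on the stage contrast.** Take 37 first-line Stage 4 patients and the 16 first-line Stage 1/2 patients at 12 µg/kg/day in the interim count (Protocol 3.7.2), with true incidence 10% in both. Summing the two binomial distributions, the probability that the observed Stage 4 rate exceeds the Stage 1/2 rate is 52% at s = 1, 75% at s = 0.5, 87% at s = 0.25 and 98% at s = 0.

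**The case against.** The strongest reply is that earlier patients were not left unasked. Protocol 10.5 has every patient questioned about health problems at each clinic visit with a non-leading question, and all AEs are reportable from first dose to 30 days after the last infusion. The change is from an open question to a directed one. A reader might infer that Stage 4 rates must rise by construction, or that the zero-capture figures are the expected result. The documents support neither: at s = 1 there is no dilution, and Stage 4 comes out higher about half the time.

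Other points also stand. The Kaplan-Meier curves count only Grade 2 or higher events and are not drawn by stage or formulation; symptomatic loss of that degree may depend less on prompting. The AESI has no color-vision term, so color complaints drawn out by the new question do not enter it unless coded to an acuity term. The boundary is blurred: treatment has no maximum duration, so some Stage 2 patients may have continued past February 2017, and selected Stage 2 AML patients received lyophilized drug (SAP 1.2.1). The by-stage display already separates first-line Stages 1/2 from Stage 4, and no formal safety comparison of formulations is planned.

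None of this removes the gap. One AESI term, abnormal visual acuity tests, needs a test to be done, and the Grade 2 referral trigger in Protocol 8.11 matches the Kaplan-Meier grade threshold. The by-stage display does not correct the difference in ascertainment. It is where a reader would mistake that difference for a drug effect.

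**Conclusion.** The SAP pools and displays the visual-acuity AESI across a change in ascertainment that it does not mention. The likely direction is a pooled rate biased low and a first-line Stage 4 versus Stage 1/2 contrast biased upward. The size is unknown and may be nil. At an assumed 10% incidence and 50 AML patients, the all-patient rate would be about 6.4–7.0% with half capture beforehand and 2.7–4.0% with none. The lower pair is an extreme that the general AE question makes implausible.

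The conclusion rests on the Amendment 9 list meaning that directed questioning was new, and on the general AE question having applied from the start. A reader might go further and drop earlier patients from the denominator, or start risk time at the first vision assessment. The documents do not support either step. SAP 2.1 makes the Safety Population primary for safety, real visual events in earlier patients would be lost from the main table, and the first vision assessment is at screening (Protocol Table 7), before any treatment-emergent event can occur. This is an inexpensive improvement to reporting; no efficacy conclusion depends on it.

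**What to change.** In SAP 4.4.2:

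1. Keep the all-patient Safety Population table for the visual AESI, with a footnote that directed questioning began with Amendment 9 and that earlier events came from general AE questioning.
2. Add labelled columns, and a matching Grade 2 or higher Kaplan-Meier, that separate patients first dosed under Amendment 9 or later from those first dosed before it. Risk time starts at first dose in both groups.
3. Show patients whose treatment straddles the amendment with the earlier group or in their own column, and state which.
4. Base any by-stage or frozen-versus-lyophilized statement on visual events only on patients under directed monitoring.

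The cost is a footnote, one extra column and one extra curve. The denominators will be small, and few frozen-drug patients may remain for the formulation comparison: at most the Stage 3 patients, and any R/R Stage 4 patients given frozen drug, who were first dosed under the amendment. If so, the report should say that the data cannot support that comparison.
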